APPENDIX E: Events of Clinical Interest Reference Table

Pneumonitis (reported as ECI if \geq Grade	2)				
Acute interstitial pneumonitis	Interstitial lung disease	Pneumonitis			
Colitis (reported as ECI if \geq Grade 2 or an	ny grade resulting in dose modification or	r use of systemic steroids to treat the AE)			
Intestinal Obstruction	Colitis	Colitis microscopic			
Enterocolitis	Enterocolitis hemorrhagic	Gastrointestinal perforation			
Necrotizing colitis	Diarrhea				
Endocrine (reported as ECI if \geq Grade 3	or ≥ Grade 2 and resulting in dose modif	ication or use of systemic steroids to treat			
the AE)					
Adrenal Insufficiency	Hyperthyroidism	Hypophysitis			
Hypopituitarism	Hypothyroidism	Thyroid disorder			
Thyroiditis	Hyperglycemia, if ≥Grade 3 and associated with ketosis or metabolic acidosis (DKA				
Endocrine (reported as ECI)					
Type 1 diabetes mellitus (if new onset)					
Hematologic (reported as ECI if \geq Grade AE)	3 or any grade resulting in dose modifica	ntion or use of systemic steroids to treat the			
Autoimmune hemolytic anemia	Aplastic anemia	Thrombotic Thrombocytopenic Purpura (TTP)			
Idiopathic (or immune) Thrombocytopenia Purpura (ITP)	Disseminated Intravascular Coagulation (DIC)	Haemolytic Uraemic Syndrome (HUS)			
Any Grade 4 anemia regardless of underlyin	_				
Hepatic (reported as ECI if \geq Grade 2, or	any grade resulting in dose modification or	use of systemic steroids to treat the AE)			
Hepatitis	Autoimmune hepatitis	Transaminase elevations (ALT and/or AST			
Infusion Reactions (reported as ECI for a	ny grade)				
Allergic reaction	Anaphylaxis	Cytokine release syndrome			
Serum sickness	Infusion reactions	Infusion-like reactions			
Neurologic (reported as ECI for any grad	e)				
Autoimmune neuropathy	Guillain-Barre syndrome	Demyelinating polyneuropathy			
Myasthenic syndrome					
Ocular (report as ECI if ≥ Grade 2 or any	y grade resulting in dose modification or	use of systemic steroids to treat the AE)			
Uveitis	Iritis				
Renal (reported as ECI if ≥ Grade 2)					
Nephritis	Nephritis autoimmune	Renal Failure			
Renal failure acute	Creatinine elevations (report as ECI if ≥G modification or use of systemic steroids to				
Skin (reported as ECI for any grade)					
Dermatitis exfoliative	Erythema multiforme	Stevens-Johnson syndrome			
Toxic epidermal necrolysis		-			
Skin (reported as ECI if ≥ Grade 3)					
Pruritus	Rash	Rash generalized			
Rash maculo-papular		-			
Any rash considered clinically significant in	the physician's judgment	1			
Other (reported as ECI for any grade)					
Myocarditis	Pancreatitis	Pericarditis			
Any other Grade 3 event which is considered immune-related by the physician					

APPENDIX F: ECI Management Algorithm

A general principle is that differential diagnoses should be diligently evaluated according to standard medical practice. Non-inflammatory etiologies should be considered and appropriately treated.

Corticosteroids are a primary therapy for immuno-oncology drug-related adverse events. The oral equivalent of the recommended IV doses may be considered for ambulatory patients with low-grade toxicity. The lower bioavailability of oral corticosteroids should be taken into account when switching to the equivalent dose of oral corticosteroids.

Consultation with a medical or surgical specialist, especially prior to an invasive diagnostic or therapeutic procedure, is recommended.

The frequency and severity of the related adverse events covered by these algorithms will depend on the immuno-oncology agent or regimen being used.

Where I-O therapy is referred, it means Ipilimumab and Nivolumab combination therapy.

In general terms, each immune-related adverse event (irAE) should be managed as follows:

- Grade I: Continue treatment as scheduled, manage with symptomatic treatment
- Grade II: Withhold therapy with I-O until improvement to grade I or better. If patient misses
 a dose of treatment drug due to an irAE, the following dose will be given as per the original
 schedule, and there will not be "catch-up" doses (i.e. treatment with I-O should not exceed
 original 26 weeks from initiation)
- If there has been no improvement within 7 days, then steroid therapy should be initiated. Dosage should be 1-2mg/kg/day of methylprednisolone IV (or equivalent) divided in 2 daily doses. The initial dosage should be continued until irAE have improved to Grade I or better. At that time, steroid should be tapered over the course of 2 weeks to the equivalent of 20 mg/day of methylprednisolone. If there has been no exacerbation of irAE with steroid taper, once the steroid dosage is 20 mg/day, as above, I-O can be resumed. Steroids should continue to be tapered off completely over a course of 2 additional weeks.
- Grades III-IV: Interrupt therapy and start steroids as per protocol above (Grade II). I-O should be resumed as described above.

If irAE persists after 3-5 days of high-dose steroids, or if it recurs after initial improvement, consideration should be given to infliximab 5 mg/kg or mycophenolate mofetil 500-750mg three times a day.

[figure not shown]
If there is recurrence of Grade III or IV irAE, subject should be removed from study.

Please follow algorithms below for specific irAE management.

Amendment9 09NOV2021 Page 61 of 77

[figure not shown]
GI Adverse Event Management Algorithm

Rule out non-inflammatory causes. If non-inflammatory cause is identified, treat accordingly and continue I-O therapy. Opiates/narcotics may mask symptoms of perforation. Infliximab should not be used in cases of perforation or sepsis.

[figure not shown]
Renal Adverse Event Management Algorithm

Rule out non-inflammatory causes. If non-inflammatory cause, treat accordingly and continue I-O therapy

[figure not shown]
Pulmonary Adverse Event Management Algorithm

Rule out non-inflammatory causes. If non-inflammatory cause, treat accordingly and continue I-O therapy. Evaluate with imaging and pulmonary consultation.

Hepatic Adverse Event Management Algorithm

Rule out non-inflammatory causes. If non-inflammatory cause, treat accordingly and continue I-O therapy. Consider imaging for

[figure not shown]

^{*}I-O therapy may be delayed rather than discontinued if AST/ALT 58x ULN and T.bill 55 x UUN.

^{**}The recommended starting dose for grade 4 hepatitis is 2 mg/kg/daymethylprednisolone IV.

[figure not shown]
Endocrinopathy Management Algorithm

Rule out non-inflammatory causes. If non-inflammatory cause, treat accordingly and continue I-O therapy. Consider visual field testing, endocrinology consultation, and imaging.

[figure not shown]
Skin Adverse Event Management Algorithm

Rule out non-inflammatory causes. If non-inflammatory cause, treat accordingly and continue I-O therapy.

Neurological Adverse Event Management Algorithm

Rule out non-inflammatory causes. If non-inflammatory cause, treat accordingly and continue HO therapy.

Patients on IV steroids may be switched to an equivalent dose of oral corticosteroids (e.g. prednisone) at start of tapering or earlier, once sustained clinical improvement is observed. Lower bioavailability of oral corticosteroids should be taken into account when switching to the equivalent dose of oral corticosteroids.

Amendment9 09NOV2021 Page 68 of 77

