5.6 Management Algorithms for Immuno-Oncology Agents

Immuno-oncology (I-O) agents are associated with adverse events that can differ in severity and duration than adverse events caused by other therapeutic classes. Nivolumab and ipilimumab are considered immuno-oncology agents in this protocol. Management algorithms have been developed to assist investigators in assessing and managing the following groups of adverse events: Gastrointestinal, Renal, Pulmonary, Hepatic, Endocrinopathies, Skin, and Neurological.

Early recognition and intervention are recommended according to the management algorithms; and in addition include ophthalmologic evaluations for any visual symptoms in order to evaluate for nivolumab or ipilimumab related uveitis.

The recommendations are to follow the algorithms in the nivolumab investigator brochure for immune related events; while the ipilimumab investigator brochure contains similar algorithms, the algorithms in the nivolumab brochure have been aligned to accommodate combinations as well as nivolumab monotherapy. Therefore, the algorithms recommended for utilization are in Appendix G for reference.

For subjects expected who require more than 4 weeks of corticosteroids or other immunosuppressants to manage an adverse event, consider the following recommendations

- Antimicrobial/antifungal prophylaxis per institutional guidelines to prevent opportunistic infections such as Pneumocystis jiroveci and fungal infections.
- Early consultation with an infectious disease specialist should be considered. Depending on the presentation, consultation with a pulmonologist for bronchoscopy or a gastroenterologist for endoscopy may also be appropriate.
- In patients who develop recurrent adverse events in the setting of ongoing or prior immunosuppressant use, an opportunistic infection should be considered in the differential diagnosis.

Additional details on the safety of nivolumab and ipilimumab, including results from clinical studies, are available in the IB.

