5.8 Criteria to Resume Treatment

Subjects may resume treatment with study drug when the drug-related AE(s) resolve to Grade ≤1 or baseline value, with the following exceptions:

- Subjects may resume treatment in the presence of Grade 2 fatigue
- Subjects who have not experienced a Grade 3 drug-related skin AE may resume treatment in the presence of Grade 2 skin toxicity
- Subjects with baseline Grade 1 AST/ALT or total bilirubin who require dose delays for reasons other than a 2-grade shift in AST/ALT or total bilirubin may resume treatment in the presence of Grade 2 AST/ALT OR total bilirubin
- Subjects with combined Grade 2 AST/ALT AND total bilirubin values meeting discontinuation parameters (Section 5.9) should have treatment permanently discontinued
- Drug-related pulmonary toxicity, diarrhea, or colitis, must have resolved to baseline before treatment is resumed
- Drug-related endocrinopathies adequately controlled with only physiologic hormone replacement may resume treatment

If the criteria to resume treatment are met, the subject should restart treatment at the next scheduled timepoint per protocol. However, if the treatment is delayed past the next scheduled timepoint per protocol, the next scheduled timepoint will be delayed until dosing resumes.

If treatment is delayed > 6 weeks, the subject must be permanently discontinued from study therapy, except as specified in discontinuation Section 5.9.

Peripheral blood and stool sample collection will continue to take place for subjects discontinued from the study up to 18 months post ASCT and/or relapse, if it occurs.

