5.9 Discontinuation Criteria

Treatment should be permanently discontinued for the following:

 Any Grade 2 drug-related uveitis or eye pain or blurred vision that does not respond to topical therapy and does not improve to Grade 1 severity within the re-treatment period OR requires systemic treatment

Amendment9 09NOV2021 Page 30 of 77

- Any Grade 3 non-skin, drug-related adverse event lasting > 7 days, with the following exceptions for drug-related laboratory abnormalities, uveitis, pneumonitis, bronchospasm, diarrhea, colitis, neurologic adverse event, hypersensitivity reactions, and infusion reactions
 - Grade 3 drug-related uveitis, pneumonitis, bronchospasm, diarrhea, colitis, neurologic adverse event, hypersensitivity reaction, or infusion reaction of any duration requires discontinuation
 - Grade 3 drug-related laboratory abnormalities do not require treatment discontinuation except those noted below
 - Grade 3 drug-related thrombocytopenia > 7 days or associated with bleeding requires discontinuation
 - Any drug-related liver function test (LFT) abnormality that meets the following criteria require discontinuation:
 - AST or ALT > 8 x ULN
 - Total bilirubin > 5 x ULN
 - Concurrent AST or ALT > 3 x ULN and total bilirubin > 2 x ULN
- Any Grade 4 drug-related adverse event or non-hematological laboratory abnormality, except for the following events which do not require discontinuation:
 - o Isolated Grade 4 amylase or lipase abnormalities that are not associated with symptoms or clinical manifestations of pancreatitis and decrease to < Grade 4 within 1 week of onset.
 - Isolated Grade 4 electrolyte imbalances/abnormalities that are not associated with clinical sequelae and are corrected with supplementation/appropriate management within 72 hours of their onset
- Any dosing interruption lasting > 6 weeks with the following exceptions:
 - Dosing interruptions to allow for prolonged steroid tapers to manage drug-related adverse events are allowed. Prior to re-initiating treatment in a subject with a dosing interruption lasting > 6 weeks, the Investigator must be consulted. Tumor assessments should continue as per protocol even if dosing is interrupted

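### Appendix F tells sites to resume ipilimumab and nivolumab after a first grade III-IV immune event, including events for which section 5.9 ends treatment permanently

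*Combined protocol and SAP*

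**What the plan says.** Appendix F defines I-O therapy as the two drugs together and gives general rules for each immune-related event. For the higher grades the rule is "Grades III-IV: Interrupt therapy and start steroids as per protocol above (Grade II). I-O should be resumed as described above". The resumption point it refers back to is in the preceding text: improvement to grade I or better, a taper over two weeks without exacerbation, and then "once the steroid dosage is 20 mg/day, as above, I-O can be resumed". The appendix adds "If there is recurrence of Grade III or IV irAE, subject should be removed from study" and sends the reader on to organ-specific algorithms.

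Section 5.9 lists the events that end treatment permanently. They include:

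- "Any Grade 4 drug-related adverse event or non-hematological laboratory abnormality, except for the following events which do not require discontinuation". The two exceptions are isolated amylase or lipase abnormalities and isolated electrolyte abnormalities, each under stated conditions.
- "Grade 3 drug-related uveitis, pneumonitis, bronchospasm, diarrhea, colitis, neurologic adverse event, hypersensitivity reaction, or infusion reaction of any duration requires discontinuation".
- "Any Grade 3 non-skin, drug-related adverse event lasting > 7 days", with separate rules for laboratory abnormalities.

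Section 5.8 sets the criteria for restarting after a delay, among them "Drug-related pulmonary toxicity, diarrhea, or colitis, must have resolved to baseline before treatment is resumed".

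**The concern.** The Appendix F bullet makes no exception and does not mention section 5.9. A site that opens the management appendix during an acute event and follows the bullet would give both drugs again after a first grade 4 immune event, or after grade 3 pneumonitis, colitis or uveitis, once the event had improved and steroids were down to 20 mg/day. The protocol has already decided that these events end treatment, and the phase IIA definition of unacceptable toxicity in section 8.6 repeats the same criteria. What is at stake is the safety of the individual patient who is re-dosed. The trial's statistical operating characteristics are not at stake.

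**Working it through.** No sample size, error rate or event rate enters this point, so the check is a comparison of texts.

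**Step 1. Does the bullet cover a first event?** Yes. Removal from study is tied to recurrence of a grade III or IV event, so resumption is what the appendix prescribes the first time.

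**Step 2. Compare the instructions by event type.**

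| First drug-related immune event | Section 5.9 | Appendix F general bullet | Conflict |
|---|---|---|---|
| Grade 4, clinical | Discontinue | Resume after taper | Yes |
| Grade 3, one of the eight named types, any duration | Discontinue | Resume after taper | Yes (Appendix G settles two types; step 3) |
| Grade 3, other non-skin and non-laboratory, over 7 days | Discontinue | Resume after taper | Yes |
| Grade 3, unlisted, resolving within 7 days | Not required | Resume after taper | No |
| Grade 3 skin | Not required | Resume after taper | No |
| Grade 4 isolated amylase/lipase or electrolyte, meeting the stated conditions | Not required | Resume after taper | No |

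Section 5.9 also discontinues for certain laboratory findings: grade 3 thrombocytopenia lasting more than 7 days or with bleeding, and liver tests beyond stated limits. The table leaves these out, so it slightly understates the overlap.

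**Step 3. Does another part of the appendices settle the conflict?** Take the eight grade 3 types in section 5.9.

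- Hypersensitivity and infusion reaction (2): Appendix G permanently discontinues at grade 3 or 4, in agreement with section 5.9.
- Pneumonitis, bronchospasm, diarrhea, colitis and neurologic events (5): these fall in organ groups that have an algorithm, but the flowcharts are not visible in the text available.
- Uveitis (1): no organ algorithm.

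The split is 2 + 5 + 1 = 8. Section 5.6 names seven organ groups, "Gastrointestinal, Renal, Pulmonary, Hepatic, Endocrinopathies, Skin, and Neurological", and the algorithm titles in Appendix F match. None is for the eye or the heart. Myocarditis is an event of clinical interest in Appendix E. For grade 3-4 uveitis and grade 4 myocarditis, the general bullet is therefore the only Appendix F dosing instruction that can be read, and it says to resume.

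**Step 4. Does the resumption threshold agree with section 5.8?** Not for pulmonary toxicity, diarrhea or colitis. Section 5.8 requires a return to baseline, whereas the appendix accepts grade I with steroids tapered to 20 mg/day.

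**Step 5. Is precedence stated?** No sentence says that section 5.9 overrides Appendix F. Section 5.6 also refers sites to Appendix G for the organ algorithms. Appendix G covers infusion reactions, and the algorithms are in Appendix F.

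**Step 6. Does the conflict reach the stopping rule?** No. The phase IIA definition in section 8.6 counts the patient when the event occurs, whether or not treatment is later resumed.

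**The case against.** The strongest reply is that the governing rule is already in the protocol body. Section 5.9 was written for this decision, section 5.8 defers to it twice, and section 5.6 describes the algorithms as help and recommendations for investigators. The bullet itself is introduced as a general statement. The ordinary reading puts a specific body section above a general appendix line, and section 5.9 does cover both uveitis and grade 4 myocarditis.

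The unseen flowcharts may also agree with section 5.9. The one legible fragment, a footnote to the hepatic algorithm, speaks of delaying rather than discontinuing up to certain liver-test limits, which implies that this algorithm discontinues beyond them. If the garbled characters are read as less-than-or-equal signs, the limits match the 8 and 5 times the upper limit of normal in section 5.9. That reading is an inference.

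Much of this stands. An experienced investigator would probably follow section 5.9, and missing figures cannot be counted against the plan. It does not remove the conflict. Precedence is left to be inferred where a safety instruction should state it. The flowcharts named in section 5.6 do not include the eye or the heart. If they do agree with section 5.9, the bullet contradicts its own appendix as well as the body of the protocol. The wrong cross-reference in section 5.6 is clerical and would not matter alone.

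**Conclusion.** The concern holds. As written, the general bullet directs re-dosing with both drugs after first events for which section 5.9 requires permanent discontinuation. The conflict covers clinical grade 4 immune events, the eight named grade 3 types apart from the two that Appendix G already handles correctly, and other non-skin, non-laboratory grade 3 events lasting more than 7 days. For five of the remaining six grade 3 types, the practical effect depends on flowcharts that could not be read. For uveitis, as for grade 4 myocarditis, no titled algorithm is available to correct the bullet. The documents give no rate of clinical grade 3-4 immune events after transplant at this dose, so the number of patients exposed cannot be estimated. The conclusion assumes only that the printed text is what sites receive.

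**What to change.** Make four changes in one amendment:

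1. Reword the bullet along these lines: *for grades III-IV, interrupt both drugs and start steroids; stop permanently if the event meets section 5.9; otherwise restart only when the section 5.8 criteria are met.* Citing section 5.9 as a whole also brings in its thrombocytopenia and liver-test limits.
2. Add a sentence at the head of Appendix F stating that section 5.9 governs wherever the two differ.
3. Correct the section 5.6 reference from Appendix G to Appendix F.
4. Check the seven organ flowcharts against section 5.9.

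The cost is one bullet, one sentence, one cross-reference, the flowchart check and a memo to sites. Sections 5.9 and 8.6, the sample size and the visit schedule stay as they are.

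### For immune events with no organ algorithm, Appendix F says to resume nivolumab and ipilimumab where section 5.9 stops them permanently, and no text says which prevails

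*Combined protocol and SAP*

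**What the plan says.** Before its organ-specific flowcharts, Appendix F sets out a general rule for every immune-related event. At Grade II both drugs are held. The rule continues: "If there has been no improvement within 7 days, then steroid therapy should be initiated". The steroid is methylprednisolone 1-2 mg/kg/day, tapered over two weeks once the event is Grade I or better. If there is no flare during the taper, then "once the steroid dosage is 20 mg/day, as above, I-O can be resumed". For higher grades the rule is "Grades III-IV: Interrupt therapy and start steroids as per protocol above (Grade II). I-O should be resumed as described above". A subject comes off only at a second severe event: "If there is recurrence of Grade III or IV irAE, subject should be removed from study".

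Section 5.9 opens with "Treatment should be permanently discontinued for the following". Its list includes:

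- "Any Grade 4 drug-related adverse event or non-hematological laboratory abnormality, except for the following events which do not require discontinuation", the exceptions being certain isolated amylase/lipase and electrolyte abnormalities;
- "Grade 3 drug-related uveitis, pneumonitis, bronchospasm, diarrhea, colitis, neurologic adverse event, hypersensitivity reaction, or infusion reaction of any duration requires discontinuation";
- other Grade 3 non-skin drug-related events that last more than 7 days, with laboratory abnormalities handled separately;
- Grade 2 uveitis, eye pain or blurred vision that fails topical therapy and "does not improve to Grade 1 severity within the re-treatment period OR requires systemic treatment".

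Section 5.6 names seven algorithm groups (gastrointestinal, renal, pulmonary, hepatic, endocrine, skin, neurological) and places the algorithms in Appendix G. Appendix G covers infusion reactions. The algorithms are in Appendix F.

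**The concern.** A site treating a listed immune event outside the seven groups finds two instructions that cannot both be followed. One gives both drugs again after steroids; the other stops them for good. The recurrence sentence shows that Appendix F intends re-treatment after a first Grade III or IV event, so this is not a slip in a single line. At stake is re-exposure of a patient to combined checkpoint inhibition after, for example, a Grade 4 myocarditis or a Grade 3 uveitis. Sites may also handle the same event differently.

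**Working it through.** No calculation in the plan bears on this, so the check is mainly a comparison of texts.

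**1. Which events depend on the general rule alone.** Appendix F titles the same seven algorithms that 5.6 lists. None is for the eye, heart or pancreas. Appendix E nevertheless lists uveitis, iritis, myocarditis, pericarditis and pancreatitis as events of clinical interest. The general rule is the only readable Appendix F instruction for these.

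**2. Whether 5.9 reaches them.** Section 5.9 applies to drug-related events. Section 3.2.5 describes immune-related events as ones that investigators judged causally related to the drug, so the two texts overlap.

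**3. Side by side.** In the last column, resumption always assumes improvement to Grade I or better and no flare during the taper.

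| Event | Section 5.9 | Appendix F general rule |
|---|---|---|
| Grade 4 uveitis, myocarditis or pericarditis | permanent stop | steroids, then resume |
| Grade 3 uveitis, any duration | permanent stop | steroids, then resume |
| Grade 3 myocarditis or pericarditis, more than 7 days | permanent stop | steroids, then resume |
| Grade 3 myocarditis or pericarditis, 7 days or less | no automatic stop; investigator judgment | steroids, then resume (no direct conflict) |
| Grade 2 uveitis, eye pain or blurred vision needing systemic treatment | permanent stop | systemic steroids, then may resume |

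Four of the five rows conflict.

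**4. Whether any text ranks the two.** Section 5.8 refers to 5.9 only for combined Grade 2 transaminase and bilirubin values and for delays beyond 6 weeks. Appendix F sends the reader from its general rule to the organ algorithms and does not mention 5.9. Section 5.6 describes the algorithms as recommended and does not say that 5.7 to 5.9 override them. I found no ranking.

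**5. Whether the 6-week limit blocks re-dosing.** Sections 5.8 and 5.9 end treatment after an interruption longer than 6 weeks. Section 5.9 exempts interruptions for prolonged steroid tapers, provided the Investigator is consulted. The events at issue are those treated with steroids, so the limit cannot be relied on.

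**6. Size.** Section 3.1.5 gives uveitis as below 1.0% of patients, with no split by grade. Taking 1.0% as a ceiling and assuming that it carries over to this population:

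- one Phase IIA cohort of 37: expected cases below 37 × 0.01 = 0.37; chance of at least one below 1 − 0.99^37 = 0.311;
- all four cohorts, 148 patients: expected cases below 148 × 0.01 = 1.48; chance of at least one below 1 − 0.99^148 = 0.774.

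These are ceilings for all reported uveitis. Cases in the conflicting rows are a subset of unknown size. The protocol gives no rate for myocarditis or pericarditis.

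**The case against.** The strongest reply is that a careful reader would follow 5.9. It is the section that defines discontinuation, and for Grade 3 uveitis its wording is a requirement. Section 5.6 presents the algorithms as help for investigators, and Appendix F introduces its rule as general guidance. Resumption under Appendix F is conditional, and 5.9 also lets the investigator stop treatment for any event judged a substantial risk. All of this stands, and it makes the conflict less even than the bare sentences suggest. It still leaves the order of precedence to inference, while Appendix F plainly directs resumption after a first severe event.

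Four stronger readings are tempting and are not supported.

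- *The conflict extends to the seven organ systems with flowcharts.* The flowcharts are not shown in the available text and may contain their own stopping steps. One figure within the general text is also not shown, and its content is unknown.
- *The choice of text alters the Phase IIA toxicity stopping count.* Section 8.6 repeats the 5.9 criteria, and Grade 3 and 4 events meeting them count whether or not drug is resumed. The count could differ only for Grade 2 uveitis with no improvement at 7 days that would later have settled on topical therapy alone. That is too narrow to argue from.
- *Sites will re-dose.* The documents show only that one instruction, taken literally, tells them to.
- *The 31% and 77% figures are the chance of a conflicting case.* They cover uveitis without regard to grade, and the second assumes that all four cohorts expand.

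The wrong appendix letter in 5.6 is editorial on its own, since the title of Appendix F identifies its content. It matters a little more here because 5.6 is where a ranking would be expected.

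**Conclusion.** The inconsistency is real and confined to immune-related events without an organ algorithm. For these, Appendix F's general rule provides for resumption in cases where 5.9 requires permanent discontinuation, and no readable text settles the order, although the tone of 5.6 and Appendix F favours 5.9. Few patients would be affected: fewer than 0.37 uveitis cases are expected per 37-patient cohort even at the 1.0% ceiling, and only some of those would fall in a conflicting row. The frequency of cardiac events cannot be sized from the documents. The consequence for a patient who is affected could be serious, so this should be corrected. It is a safety-wording matter and does not undermine the efficacy analysis or the stopping boundaries. The conclusion assumes that the figures not shown contain no precedence statement and no eye or heart algorithm.

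**What to change.** 1. In 5.6, and again at the head of Appendix F's general text, state that sections 5.7 to 5.9 govern delay, resumption and discontinuation and prevail over Appendix F.
2. Replace the second sentence of the Grades III-IV line with: *I-O may be resumed as described above only if 5.8 is met and no 5.9 discontinuation criterion applies.*
3. Add the same condition to the Grade II steroid bullet. This covers Grade 2 ocular events that need systemic treatment.
4. In 5.6, correct the pointer from Appendix G to Appendix F.

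The condition should refer to 5.9 and not restate it. A blanket sentence that all Grade 4 events are discontinued would drop 5.9's amylase/lipase and electrolyte exceptions and create a new conflict. The recurrence sentence can stay, because it would then apply only to events that 5.9 allows to resume.

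The cost is a wording amendment to 5.6 and Appendix F. It adds no visits or tests and leaves the rules in 5.7 to 5.9 and 8.6 unchanged.

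### The general rule in Appendix F resumes both drugs after a first Grade III-IV immune event even where Section 5.9 stops treatment permanently, and no general sentence says which governs

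*Combined protocol and SAP*

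**What the plan says.** Section 5.9 lists the grounds for permanent discontinuation. Two matter here. The first is "Any Grade 4 drug-related adverse event or non-hematological laboratory abnormality, except for the following events which do not require discontinuation"; the exceptions are isolated amylase or lipase abnormalities and isolated electrolyte abnormalities, each under conditions. The second is "Grade 3 drug-related uveitis, pneumonitis, bronchospasm, diarrhea, colitis, neurologic adverse event, hypersensitivity reaction, or infusion reaction of any duration requires discontinuation".

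Appendix F gives a general rule by grade for each immune-related event, and defines I-O as the ipilimumab and nivolumab combination. At Grade II, treatment is held. If there is no improvement within 7 days, steroids are given until the event is Grade I or better, then tapered over 2 weeks to 20 mg/day of methylprednisolone or equivalent. If the event has not flared by then, I-O can restart. For higher grades the rule is "Grades III-IV: Interrupt therapy and start steroids as per protocol above (Grade II). I-O should be resumed as described above". The text goes on: "If there is recurrence of Grade III or IV irAE, subject should be removed from study". It then directs the reader to the organ algorithms.

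Section 5.6 says that these algorithms exist to "assist investigators in assessing and managing the following groups of adverse events: Gastrointestinal, Renal, Pulmonary, Hepatic, Endocrinopathies, Skin, and Neurological". It presents them as recommendations and locates them in Appendix G, although they stand in Appendix F.

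Two other places agree with Section 5.9. Section 5.8 says: "Subjects with combined Grade 2 AST/ALT AND total bilirubin values meeting discontinuation parameters (Section 5.9) should have treatment permanently discontinued". Appendix G permanently discontinues treatment after a Grade 3 or 4 infusion reaction.

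**The concern.** Appendix F is the part of the protocol that a site is likely to open while managing an immune event. For a first Grade 4 event, or a first Grade 3 uveitis, its general rule leads back to dosing with both drugs, and its wording is an instruction rather than a permission. Section 5.9 says that the same patient must not be treated again. What is at stake is re-exposure to the combination after a severe immune toxicity, and different handling of the same event at the two recruiting centers. Whichever text an investigator follows, the other has been breached.

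**Working it through.** No arithmetic applies. The check sets the texts side by side.

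**1. Does the general rule reach a first event?** Yes. Its only removal clause is for recurrence. Resumption does depend on recovery, the taper and the absence of a flare. Those conditions do not bring it into line with Section 5.9, where a listed event ends treatment whether or not the patient recovers.

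**2. Where do the two rules differ, and could an organ algorithm resolve it?** All events below are taken as drug-related.

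| First event | Section 5.9 | Appendix F general rule | Own organ algorithm? | Result |
|---|---|---|---|---|
| Grade 3 uveitis | Permanent stop, any duration | Resume after recovery and taper | None | Contradiction |
| Grade 4 uveitis or myocarditis | Permanent stop | Resume after recovery and taper | None | Contradiction |
| Grade 3 colitis, pneumonitis or neurologic event | Permanent stop, any duration | Resume, but organ algorithm to be followed | Yes, not shown | No conclusion |
| Grade 3 skin event | No stop on grade alone | Resume | Yes, not shown | General rule compatible |
| Grade 3 or 4 infusion reaction | Permanent stop | Appendix G applies: permanent stop | Not needed | Agreement |

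Appendix E lists uveitis under ocular events and myocarditis under other events. Neither is in the seven groups named in Section 5.6 and in the Appendix F algorithm headings. For them the general rule is the only dosing instruction in the visible text of Appendix F. Pancreatitis is also listed under other events, but the gastrointestinal chart might cover it, so it is not used as an example.

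**3. Does any sentence rank the two?** Section 5.8 refers to Section 5.9 twice: once for combined Grade 2 liver values and once for delays beyond 6 weeks. Appendix G covers infusion reactions. Section 5.6 calls the algorithms recommended. None of these is a general statement that Section 5.9 prevails, and the Appendix F text does not mention Section 5.9.

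**4. Does it reach the statistical design?** The definition of unacceptable toxicity in Section 8.6 repeats the Section 5.9 events for Phase IIA and counts them whatever is decided about dosing. The Phase Ib rule counts Grade 4 or higher non-hematologic toxicities, with the Section 5.9 exceptions. Neither count depends on whether the patient restarts.

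**5. The hepatic footnote.** The extracted text reads "I-O therapy may be delayed rather than discontinued if AST/ALT 58x ULN and T.bill 55 x UUN". Assume that the damaged figures mean at most 8 x and at most 5 x ULN. The footnote then respects two of the three liver limits in Section 5.9 (AST or ALT above 8 x; bilirubin above 5 x). It could miss only the third: "Concurrent AST or ALT > 3 x ULN and total bilirubin > 2 x ULN". The largest possible overlap is AST or ALT above 3 and up to 8 x ULN together with bilirubin above 2 and up to 5 x ULN. The flowchart box that carries the asterisk is not shown and may be narrower.

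**The case against.** The strongest reply is that the hierarchy is clear enough already. Appendix F describes its rules as general, and Section 5.6 presents the algorithms as aids. Section 5.9 is the dedicated rule and names Grade 3 uveitis specifically. Sections 5.8 and 8.6 and Appendix G all follow it, and Section 5.9 also lets the investigator stop treatment for any event judged a substantial risk. Section 7.0 adds real-time monitoring and weekly safety review. Much of the Grade III rule is legitimate too: skin events, most laboratory abnormalities and many non-skin events lasting 7 days or less do not require a stop.

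Most of this stands as evidence of intent, and the sponsor probably means Section 5.9 to govern. It does not remove the contradiction. The lead sentence of Section 5.9 and the Appendix F rule both use *should*, so the verb alone does not rank them. The only onward reference in Appendix F is to the organ algorithms, and there is none for uveitis or myocarditis.

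The objection does succeed against three wider inferences that a reader might draw:

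- **Conflict in every organ group.** This cannot be shown for the seven groups whose flowcharts are missing from the text.
- **The hepatic footnote as a second contradiction.** That would rest on damaged figures and an unseen box, and Section 5.8 already covers combined Grade 2 values.
- **A size in doses or patients.** Any count of remaining doses depends on an invented event date and recovery time. The Grade 3-4 rate from the melanoma combination trial in Section 2.2 comes from another population and several dose levels. The commonest events named there are laboratory ones, which Section 5.9 mostly does not discontinue at Grade 3.

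**Conclusion.** Wrong as written: an internal contradiction in a safety rule. For a first Grade 4 drug-related event outside the seven organ groups (apart from the two laboratory exceptions), and for a first Grade 3 uveitis, the general rule in Appendix F directs resumption of both drugs and Section 5.9 forbids it. The documents give no frequency for these events, so no number of patients is claimed.

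The conclusion rests on the visible text. An unlabelled figure beside the general rule is not shown; if it carries a cross-reference to Section 5.9, the point falls away. The hepatic footnote remains a point to check in the original. A reader might also infer that the toxicity boundaries are compromised. They are not: Section 8.6 counts the events independently of dosing, so boundaries, power and event counts are unchanged.

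**What to change.** In the next amendment:

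- Add to the Grades III-IV line of Appendix F: *unless Section 5.9 requires permanent discontinuation*.
- Add at the head of Appendix F: *The resumption and permanent discontinuation criteria in Sections 5.8 and 5.9 take precedence over the general rules and algorithms below.*
- Compare the marked hepatic box in the original with the concurrent liver criterion in Section 5.9. Amend the footnote only if the box would allow delay where that criterion is met.
- Correct the pointer in Section 5.6 from Appendix G to Appendix F at the same time.

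The cost is one clause, one sentence and a corrected cross-reference. No patients, visits or tests are added, and Section 8.6 needs no change.
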